## Outcomes

**Aim 1** qualitative interviews will assess patient and family experiences across a number of domains related to asthma health care decision making and outcomes in HDHPs (RQ-6, PC-3). These domains have been selected based on patient concerns and interests expressed in our prior surveys, qualitative interviews, and focus groups with HDHP members and asthma patients; suggestions from AAFA co-investigator [name]; and postings from readers of [name] asthma blog (url: <http://asth.ma>) (RQ-6). Domains and interview questions will be refined based on input from the project’s Stakeholder Advisory Board and Patient and Family Research Council. Given the limitations of claims data for understanding the perceptions and experiences of patients, these patient-reported qualitative outcomes will provide complementary, in-depth insight into decision making about health and financial outcomes that matter most to patients. See Appendix for the draft interview guide. Area to be explored will include:

1. Understanding and perceptions of insurance benefits (understanding cost-sharing requirements, especially for asthma medications, awareness of having a PDL, perceptions about PDL usefulness for asthma medications)
2. Impact of cost barriers on health care use for asthma, especially medications (decision making around delaying or forgoing care due to cost and for which types of services, patient-defined adverse consequences related to asthma care and disease burden)
3. Financial burden of asthma care (OOP cost burden from asthma care, other unmet medical or non-medical needs due to paying for asthma care, other patient-defined adverse consequences, strategies to reduce OOP barriers for asthma care, experiences discussing cost barriers with providers)
4. Intra-familial trade-offs (impact on asthma care needs, other family members’ medical and non-medical needs)

Interviews will also explore non-financial barriers to adherence faced by families with asthma, such as low parental expectations for symptom control, concern about side effects, competing household priorities, and lack of routines for medication administration. We will also explore the relative importance of financial vs. non-financial barriers to adherence to asthma medications.

The primary study outcomes for **Aims 2-4** are the claims-based measures of asthma medication use, outcomes, and OOP costs listed below, measured at the individual level. Our project focuses on these patient-centered, clinically-relevant outcomes (RQ-6), and will not focus on total costs to employers and the health care system.

1. Adherence to controller medications (Aims 2-3): We will assess adherence to guideline-recommended asthma controller medications, including ICS, LTA, or ICS-LABA, which have been shown to reduce asthma morbidity and adverse outcomes. These medications are subject to the deductible in HSA-HDHPs without PDLs, free in HSA-

HDHPs with PDLs, and subject to copayments in traditional plans. We will measure: 1) PDC, the proportion of days that members have their medication available per month. Proportion of days covered is calculated based on the days' supply in each pharmacy fill, spread over the days following the fill. Previous studies have used proportion of days covered as a valid measure of adherence that is associated with better clinical outcomes (IR-4). 2) medication discontinuation, defined as experiencing a gap of more than 60 days in availability of a controller medication following a period of at least 180 days of continuous treatment (i.e. with no gap in availability greater than 60 days). Claims-based measures such as these have been shown to be valid measures of adherence (IR-4).

Because PDLs are not standardized nationally, there is some variation among health plans in the specific types of drugs included. From a review of several other insurers' and employers' PDLs, those that include asthma medications cover both controllers and beta agonists/rescue medications. However, some of these PDLs include a few less commonly used inhaled corticosteroids which are not included in the PDL that we propose to study. To address this variation, in addition to measuring adherence to asthma controller medications generally, we will also measure adherence to the specific controller medications included in the PDL and adherence to the sub-set of controller medications that are not included in the PDL (Aerospan, Arnuity ellipta, Asmanex HFA, Aerobid, Azmacort).

2. **Use of asthma rescue medications (Aims 2-3):** We will assess use of albuterol and levalbuterol inhalers, the primary asthma rescue medications prescribed to patients, which are subject to the deductible in HSA-HDHPs without PDLs, free in HDHPs with PDLs, and subject to copayments in traditional plans. All albuterol and levalbuterol inhalers are brand-name drugs containing 200 puffs each. We will exclude nebulized versions as these are predominantly used by younger children and do not come in standardized doses. As in our prior study, we will measure the standardized number of inhalers dispensed per month based on National Drug Code (NDC) in pharmacy claims. Given the inter-relationship between rescue and controller medication use, we will also measure the ratio of controller medications to total asthma medications, a metric for which higher values are associated with better asthma control and lower rates of asthma-related ED visits.
3. **Use of spacers and nebulizer machines (Aims 2-4):** Based on input from patients and stakeholders, and with additional input from questions from added questions in the qualitative interview guide in response, we will assess changes in the number of spacers and nebulizer machines received by study patients, based on claims data. We will measure changes in receipt of spacers and nebulizer machines after a switch to an HSA-HDHP vs. remaining in a traditional plan to see if changes in the cost-sharing for these devices leads to a decrease in receipt and an increase in OOP costs to families.
4. **Asthma-related ED visits and hospitalizations (Aims 2-3):** As a measure of potentially avoidable short-term complications, we will measure asthma-related ED visits and hospitalizations that have a primary ICD-10 diagnosis code for asthma.
5. **OOP health care costs (Aim 4):** We will calculate consumer price index (CPI)-adjusted OOP costs for asthma medications and other health services, summing deductible, co-pay, and coinsurance amounts, aggregated into annual measures. Financial burden due to OOP costs will be defined as annual family OOP costs as a percent of family income, with cutpoints of >5% and >10% to indicate financially burdensome OOP costs.

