Thus, to be included in the study, all subjects will have at least 12 months in both the Pre and Post periods. We selected a follow-up period of up to three years because we hypothesized that patients in HSA-HDHPs with PDLs might experience benefits that take longer than one year to manifest. A primary purpose of the pre period is to ensure precise matching between groups on both the level and trend in key baseline characteristics (e.g., employer characteristics, demographics, utilization patterns, etc.). Our difference-in-difference analyses will include annual-to-annual comparisons (baseline to follow-up year 1, baseline to follow-up year 2, etc.). This will allow intuitive comparisons such as "relative to controls, adherence among HSA-HDHP members with PDLs increased by 4% in follow-up year 1 compared to baseline, but by follow-up year 2, adherence had increased by 11% compared to baseline." We have used this approach in a variety of studies and find that it translates well to clinical and policy audiences. For analyses of outcomes in the second and third year post-switch, we will only include study group patients and their matched controls who have had that length of follow up. We will compare and report differences in baseline characteristics for the subgroups of study cohort members that remain enrolled for each additional year.

We will exclude those over age 64 who are eligible for Medicare. We will identify members with asthma during a 12-24-month period prior to the index date using the same claims-based algorithm used to identify HPHC members with asthma for the Aim 1 interviews, with the inclusion of ICD-9 codes 493.XX to identify a diagnosis of asthma through October 2015. This broad definition will include patients with *intermittent asthma* as well as those with *persistent asthma*, for whom controller medications are recommended. Subgroup analyses will focus on the subset of patients who meet the HEDIS definition of persistent asthma ( $\geq 1$  ED or inpatient visit with asthma as the principal diagnosis,  $\geq 4$  outpatient visits with any asthma diagnosis, or  $\geq 4$  asthma drug dispensing events in the baseline year).

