Eligible employers are those that offer only one plan type in a given benefit year: 1) traditional HMO/PPO/POS plans (deductibles  $<\$1000$ , copayments of  $<\$50$  for most services, tiered copayments for medicines); 2) HSA-HDHPs without PDLs; or 3) HSA-HDHPs with PDLs. We will select “full-replacement” employers that replace a traditional plan with an HSA-HDHP without PDL, or replace an HSA-HDHP without PDL with an HSA-HDHP with PDL, for all employees at a given point in time; matched comparison employers will include those that keep all employees in their prior plan. Including only full-replacement employers is a key strategy used in multiple previous studies to reduce member self-selection bias. The index dates for HSA-HDHP enrollees will be the dates of the employer-mandated plan switch. Matched controls will have contemporaneous enrollment in traditional plans also mandated by their employers; index dates will be assigned to be the same as matched intervention enrollees. We will also include matched controls who remain in HSA-HDHPs without PDLs. To reduce bias due to dropout, we will censor both HDHP and control patients together when either one drops out, and weight the remaining population to retain its baseline demographic and clinical profile. We estimate that there will be 621,481 adults and 310,741 children with asthma from 2004-2017 who will meet our inclusion criteria: 18,000 asthma patients in HSA-HDHPs without PDLs, 4,222 in HSA-HDHPs with PDLs, and 910,000 in traditional plans.

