## **Predictors and Covariates**

Table 2 shows the main predictors and covariates we will use in the proposed study for propensity matching to create study cohorts (CI-1, 4-5), predicting or adjusting outcomes, or stratifying analyses. Our primary predictor variables include study period and insurance type. Study period indicates the one-year period before or up to three years after the index date. Insurance type includes: 1) HSA-HDHP without PDL; 2), HSA-HDHP with PDL; and 3) traditional plan.

Other co-variates include asthma severity in the baseline period using the HEDIS definition for persistent asthma (see above under Study Population), and using chronic oral corticosteroid therapy (180+ days in the prior year) or any use of omalizumab in the baseline year to define severe asthma. To estimate co-morbidity, we will use the well-established Johns Hopkins Adjusted Clinical Groups (ACG) scores which use ICD-10 codes in the baseline period to calculate a standardized morbidity score in a specified time period. We will measure the presence of other chronic conditions from claims data in the baseline year using the Johns Hopkins ACG system. We will also measure whether enrollees have COPD as a co-morbidity, as there can be overlap with COPD and asthma, and use of similar medications.

A unique innovation of our study is the availability of data linkages (IR-2) with consumer data from a

major credit reporting company linked to insurance claims from our data vendor, Optum. Consumer data elements include total household income, net

worth, and race/ethnicity. We will combine self-reported race/ethnicity data from credit card and loan applications with data from Optum on surname analysis for identifying Hispanic or Asian ethnic groups and geocoding to derive race/ethnicity from census data. We will also use census-based indicators for neighborhood education and poverty levels. Other variables used to propensity-match cohorts and adjust for confounding will include sex and age; state/region of residence; individual versus family plan; baseline number of outpatient visits, presence of an inpatient hospitalization, and total expenditures; employer size (number of employees); and average employer baseline expenditures per capita (CI-1, 4-5).

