Asthma controller medications are intended to be taken regularly, so we will examine controller medication adherence using ITS. We will test the statistical significance of level or trend changes following insurance plan type switch using GLM models, adjusting for seasonality and first-order autocorrelation between sequential monthly measurements using the empirical sandwich estimator. Our analytic model will compare the odds ratio of having the primary therapy in the category available each day before and after the coverage switch. Our key independent variables will be: month, period (before or after the benefit switch), and month after the plan switch, adjusting for the same covariates as above. In addition to modeling changes in adherence to controller medications generally, we will address the variation across health plans in the types of controller medications included in PDLs by conducting sub-analyses to examine changes in adherence to the specific controller medications that are included in the PDL and those that are not included in the PDL (Aerospan, Arnuity ellipta, Asmanex HFA, Aerobid, Azmacort). For patients using medications that are not included in the PDL, we will examine the degree to which patients change to medications that are included on the PDL.

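### No months are set aside around the plan switch, so fills moved across it would count as plan effect, above all in the ITS level change; the size is unknown

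*Combined protocol and SAP*

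**What the plan says.** Study Population fixes the boundary: "The index dates for HSA-HDHP enrollees will be the dates of the employer-mandated plan switch". Matched controls receive the same date. Predictors and Covariates adds: "Study period indicates the one-year period before or up to three years after the index date". The two periods therefore adjoin.

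Under Outcomes, item 1 defines controller adherence: "Proportion of days covered is calculated based on the days' supply in each pharmacy fill, spread over the days following the fill". It does not say what happens to supply that overlaps an earlier fill, or to supply that straddles the index date. For rescue inhalers (item 2), "we will measure the standardized number of inhalers dispensed per month based on National Drug Code (NDC) in pharmacy claims". OOP costs (item 5) are built by "summing deductible, co-pay, and coinsurance amounts, aggregated into annual measures".

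In the Analysis plan for Aim 2, the adherence ITS is specified as follows: "Our key independent variables will be: month, period (before or after the benefit switch), and month after the plan switch". It is fitted while "adjusting for seasonality and first-order autocorrelation between sequential monthly measurements". The DiD compares the baseline year with each whole follow-up year.

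No section gives a transition, washout or phase-in period, or a sensitivity analysis without the months around the switch. Generalizability and Limitations does not mention stocking up or delayed fills.

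**The concern.** The switch changes the price of the same drugs overnight, and only for switchers. The plan puts some inhaled steroids at $140-$307 a month. A patient about to face the full deductible gains by filling early; a patient about to receive free drugs through a PDL gains by waiting. The plan treats such behaviour as real: Aim 1 asks about delaying care because of cost and about strategies to reduce cost.

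A shift confined to switchers is not removed by the DiD, by seasonality terms or by shared index dates. It falls in the last baseline and first follow-up months, which largely determine the ITS level change.

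The direction depends on contrast and outcome:

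- **Switch to an HSA-HDHP without PDL.** If overlapping supply is carried forward, stocking up hides part of the PDC fall. With or without carry-forward, it exaggerates the fall in inhalers dispensed and understates the rise in OOP costs.
- **Gain of a PDL.** Held-back fills lower the baseline and exaggerate the gain in PDC and dispensing, which is the study's central question.

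**Working it through.** **Yardstick.** Table 3 gives detectable PDC differences of 2.0 points (PDL contrast, n=4,222 vs 16,888) and 1.0 point (n=18,000 vs 72,000). With (1.96 + 0.84) x SD x sqrt(1.25/n) and an assumed SD of 0.42, these come out at 2.02 and 0.98. Treating 46% as a two-sided proportion gives 2.4 and 1.16. The plan states no SD, so the figures can be neither confirmed nor called wrong. They serve only as a scale here.

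**Upper bounds, PDC.** Share of patients x days moved / 365. The 10% share is an assumption.

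- 30 days: 0.10 x 30/365 = 0.8 points
- 60 days: 0.10 x 60/365 = 1.6 points
- 90 days: 0.10 x 90/365 = 2.5 points

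These are ceilings, because they count every moved day as a change in coverage.

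**Dispensing.** One inhaler moved across the boundary by 10% of patients adds one in one period and removes one in the other: 0.10 x 2 = 0.2 inhalers per person-year in the DiD.

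**OOP.** One controller month moved out of the follow-up year by 10% of patients: 0.10 x $140 = $14 to 0.10 x $307 = $31 per person, against a detectable $23 in the no-PDL contrast. This assumes that full price would otherwise have been paid in that year.

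**Simulation.** Day-level 30-day fills for 6,000 switchers, with controls taken as flat. PDC moves from 46% to 39% (deductible) or from 46% to 48% (PDL). Assumed behaviour: 10% or 30% of patients are prone to add 90 days at a last-month fill, or hold back fills in the last 60 days. The ITS is least squares on 24 monthly means with the plan's three terms. Each cell shows the full-window result, then the result with 91 days dropped on each side.

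| Scenario | Year-1 PDC change | ITS level change | Fills per year |
|---|---|---|---|
| Deductible, no shift | -5.9 / -6.8 | -3.5 / -6.5 | -0.76 / -0.84 |
| 10% stock up, carried forward | -5.1 / -6.8 | -1.5 / -7.0 | -0.92 / -0.85 |
| 30% stock up, carried forward | -4.0 / -6.7 | +2.4 / -4.8 | -1.38 / -0.87 |
| 10% stock up, not carried | -6.0 / -6.9 | -3.9 / -6.7 | -0.87 / -0.83 |
| 30% stock up, not carried | -6.2 / -7.0 | -4.2 / -6.7 | -1.18 / -0.86 |
| PDL, no shift | +2.0 / +2.2 | +1.6 / +2.6 | +0.25 / +0.28 |
| 10% hold fills | +2.6 / +1.8 | +4.8 / +1.4 | +0.36 / +0.23 |
| 30% hold fills | +4.3 / +2.0 | +11.2 / +2.8 | +0.66 / +0.26 |

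The windowed level changes carry visible simulation noise (-4.8 to -7.0 across the carried-forward rows).

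Separate runs with 20% of patients shifting 60 days moved the level change from about -6.0 to -3.6 (stocking up) and from about +1.2 to +7.4 (holding back). The annual PDC shift was about 0.7 to 1.9 points. Dropping the last 2 baseline and first 3 follow-up months largely restored the level. The no-shift starting values differ between the two sets of runs, so the movement should be read, not the level.

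**The case against.** **Size.** The documents contain no rate of fill-shifting, and the simple ceilings overstate the error: 10% of patients prone to add 90 days gives a ceiling of 2.5 points, but the simulated annual PDC moves by 0.8. This stands.

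**The overlap rule.** Without carry-forward, stocking up barely moves PDC (-6.0 and -6.2 against -5.9). This also stands: the PDC bias in the deductible contrast is conditional on a rule that the plan does not state. Fill counts shift under either rule.

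**Awareness and elasticity.** Holding fills requires advance knowledge of the PDL. Section D says that interview recruits may not know whether they have one, and the dissemination section expects learning over time. The limitations also describe rescue inhaler use as relatively insensitive to price. Both points lower the likely size. Neither excludes a change in timing when total use is stable.

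**Controls.** Those who remain in HSA-HDHPs may have deductible-year timing of their own, so the net direction in the PDL contrast is not certain. They still lack the incentive created by gaining a PDL.

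**Existing safeguards.** Monthly series are plotted, the DiD is meant to carry the effect estimates, and years 2 and 3 are compared with baseline. For PDC after a switch to the deductible, a 60-day stock is gone before year 2. But later years still use the affected baseline for dispensing counts and for the PDL contrast, and the plan also tests the ITS level change formally.

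**The window changes the question.** With nobody stocking up, dropping 91 days each side moves the annual estimate from -5.9 to -6.8, about as much as the 10% stocking scenario does. This is why the window belongs in an added analysis and should not replace the main one.

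**Conclusion.** The omission is clear from the text and matters if switchers move fills. The ITS level change is the exposed estimate: in the scenarios it moves by 2 points or more and can change sign, whereas the annual PDC change moves by roughly 0.6 to 2.3 points (1.98 to 2.63 at the low end, 1.98 to 4.31 at the high end). All of this rests on assumed shares and days and, for stocking up, on carry-forward of supply.

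A reader might infer more than the documents support:

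- **That the error rivals the hypothesised 1-4% PDL gain.** That figure refers to the number of fills and is not a PDC benchmark.
- **That controller and rescue results cannot be read together.** Biases of opposite sign and unknown size call for a sensitivity analysis and a caveat, not for abandoning the joint reading.
- **That OOP costs need the same window.** OOP and its burden cutpoints are annual. If the switch starts a deductible year (likely, but not stated), dropping the first months would remove part of the exposure under study.

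**What to change.** 1. State in Outcomes item 1 whether overlapping days' supply is carried forward in PDC.
2. For PDC and rescue-inhaler counts, prespecify an analysis of the ITS level change that drops the last 2 baseline and first 3 follow-up months in both arms, or gives them separate indicators. Add a matching DiD with those months omitted, with counts expressed as monthly rates because the periods become 10 and 9 months (12 - 2 and 12 - 3).
3. Report it beside the full-window result, and do not interpret the ITS level change alone if the two differ.
4. Check the baseline-trend match on the months before the window.
5. Keep annual OOP costs and burden cutpoints on full years, and note that purchases may have been moved across the boundary.

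The cost is plan wording and re-runs on existing data. The added analysis loses about 5 of 24 monthly points, so it is somewhat less precise, and it estimates the effect after the transition, not the immediate effect.
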